Lower body muscle strength will be assessed using a standard 5-repetition maximum protocol ⁴⁰ on a Cybex plate-loaded leg press calculated with the Brzycki, et al. 1-repetition maximum prediction equation ⁴¹. Participants will begin with a brief warm-up (~5 min.) on the treadmill followed by instruction on proper leg press form. After one light warm-up set (~10 repetitions) to ensure proper form, weight will be selected with the goal of achieving 5-repetition maximum. Weight will continue to be increased until the goal is reached, with 60 sec. rest between each attempt. Predicted 1-repetition maximum assessments have been used successfully in adolescents with IDD ⁴². We will use grip strength as an indicator of upper body strength. Grip strength will be measured using a hand dynamometer (Model: Jamar Plus Electronic, Patterson Medical, Warrenville, IL). Participants will be asked to stand straight with their elbows flexed at 90° and instructed to clench the handle as strong as possible. We will collect 3 measures from both their dominant and non-dominant hand, and scores from each hand will be averaged. Grip strength has been successfully used in individuals with IDD ^{43, 44}.

Motor ability

Motor ability will be assessed by the Gross Motor Quotient and Percentile obtained from Test of Gross Motor Development-second edition (TGM-2) ⁴⁵. The TGM-2 requires ~20 min. to administer and has been used in the NHANES National Youth Fitness Survey ⁴⁶, and in individuals with IDD ^{47, 48}. During the COVID 19 lockdown motor ability will be assessed remotely.

Quality of life

Quality of life will be assessed with the Personal Well-Being Index-Intellectual Disability ^{49, 50}. Cronbach alpha of 0.76, and 1- to 2-wk. test-retest reliability of 0.58 have been reported in individuals with IDD ⁴⁹.

Self-Efficacy and Social Support

Self-efficacy and social support will be assessed using the Self-Efficacy for Activity for Persons with Intellectual Disabilities Scale, and the Social Support for Activity for Persons with Intellectual Disabilities Family Scale ⁵¹. Cronbach's alpha in individuals with IDD was 0.73 for both scales. Barriers for PA will be assessed using the 12-item Barriers to and Support for PA questionnaire ⁵².

Parent's Beliefs/Attitudes Towards PA

Parent's beliefs/attitudes toward PA will be assessed with an adapted version of the Healthy Buddies Parent Nutrition and Physical Activity Survey, which has been previously used with parents of adolescents with IDD ⁵³.

Parent Time Constraints

Parent time constraints will be assessed with the Leisure Time Satisfaction Scale ⁵⁴ and parent stress scales.

Descriptive Outcomes

To characterize our study sample, we will measure weight, height, and waist circumference in adolescents and parents at baseline, 6, 12, and 18 mos. Weight will be measured in light clothing on a calibrated scale (Model #PS6600, Belfour, Saukville, WI) to the nearest 0.1 kg. Standing height will be measured with a portable stadiometer (Model: #IP0955, Invicta Plastics Limited, Leicester, UK). BMI will be calculated as weight

(kg)/height (m^2). BMI percentile for adolescents will be obtained using the CDC calculator (<http://apps.nccd.cdc.gov>). Waist circumference will be assessed using the procedures described by Lohman et al.⁵⁵. During the COVID-19 lockdown height, weight, and waist circumference will not be collected.

Process variables

Intervention fidelity. Study staff will review recordings from all scheduled exercise sessions and parent/participant meetings (A+P group). The content delivered will be compared with a checklist of scheduled activities/topics. Feedback will be provided to all health coaches, and those covering <80% of scheduled activities/topics will receive additional training and will be dismissed if the problem recurs.

Session attendance for both group exercise and adolescent/parent education/support sessions will be obtained from records maintained by the health coach, and expressed as the percent of possible sessions from 0-6 mos. and 7-12 mos.

Self-monitoring of PA will be assessed as the percentage(total days worn/ total days enrolled in the intervention) of days with Fitbit data over a minimum of 8 hrs. between 6 am and midnight (0-6, 7-12, 13-18 mos.).

Parental use of the Facebook page (A+P group) will be tracked as the frequency of posting, i.e., posts/d (initial and replies) averaged over 3 time periods: (0-6, 7-12, 13-18 mos.).

Peer interactions/support. Staff will review video recordings of a random sample (33%) of group exercise sessions to identify and classify both peer-to-peer and health coach to adolescent interactions. Interactions will be quantified and coded as verbal/non-verbal (waving, pointing, shaking head in agreement/disagreement), and as positive, neutral or negative, and relative to support, using a checklist.

Exit Interview

We will conduct structured interviews by phone with a 20% random sample of participants and parents from both intervention arms to gather information that might be useful for improving the intervention and/or implementing the intervention in settings serving adolescents with IDD. Topics will include preference for the AO or A+P interventions, reasons for missing scheduled sessions for both the parent and participant, intervention length, difficulties with compliance, suggestions for improvements and overall satisfaction with the intervention, parent's enjoyment of the exercise and educational sessions, health coaches, PA recommendations etc.

Analysis plan and statistical power

Power. This trial is powered to detect a between arm difference (AO vs. A+P) in the change of MVPA (0-6 mos.) of 10 min./d. This represents an additional 70 min. of MVPA/wk. An increase in MVPA of this magnitude is associated with improved adiposity and cardiovascular fitness in typically developing adolescents^{56, 57}, and potentially in adolescents with IDD, a group with low baseline levels of MVPA^{58, 59}. Statistical power to detect a significant effect on MVPA across 6 mos., the primary aim in the proposed 2-arm randomized design, depends on the following parameters: the number of participants in each arm (J), the number of measurements ($n = 21$; 7 days at 0, 3, and 6 mos.), correlations among repeated measures (r), and effect size (f). Assuming a conservatively large standard deviation for change in MVPA in both arms (35 min./d), corresponds to a small to moderate effect size ($f = 0.14$). The correlation between repeated measures of MVPA (3 mo. interval) in our pilot trial was $r = 0.22$. To be conservative, we assumed a higher correlation ($r = 0.25$) for this sample size calculation. Based on these assumptions, power analysis using G*Power 3.1.9.2 shows a sample of 114 adolescents ($J = 57/\text{arm}$) would provide 81% power to test overall between arm differences across time, i.e., group effect. This sample size would also provide $\geq 80\%$ power to detect a group difference in change, i.e., time-by-group interaction, as small as $f = 0.09$. Missing data will be fully recovered via multiple imputation as discussed subsequently, which will remove or minimize (if present) confounding effects of missingness on our statistical power. The secondary aims were not powered to detect between group differences.

Baseline equivalence. We will compare baseline characteristics, e.g., age, sex, race/ethnicity, BMI, IDD diagnosis, etc., between the AO and A+P arms using independent-samples *t*-test for continuous variables and chi-square/Fisher test for categorical variables, to assess the degree to which randomization resulted in equivalent groups. Variables that demonstrate a significant nonequivalence will be controlled for in our analytic models to improve the accuracy in estimates of the intervention effect. Prior to modeling, missing data for each outcome will be imputed as described subsequently.

Primary aim analysis. Our primary aim, to compare changes in MVPA (min./d) between the AO and A+P arms from 0 to 6 mos., will be evaluated using general mixed modeling for repeated measures. Specifically, the model will examine linear/nonlinear change over time (21 measurements = 7 days at each of 0, 3, and 6 mos.); i.e., time effect, overall group difference across time, i.e., group effect, and group difference in change, i.e., time-by-group interaction, controlling for day of the week (weekday/weekend) and baseline characteristics imbalanced between the groups. For example, a significant interaction will indicate that adolescents in the A+P arm achieve more minutes of MVPA compared to adolescent in the AO arm, and this difference becomes greater across time. A proper error covariance structure will be determined based on relative model fit, e.g., Akaike information criteria, adjusted Bayesian information criteria.

Secondary Aim analysis. Our secondary aim, to compare changes between the AO and A+P arms on the following variables across 18 mos.: 1) MVPA (min./d) and sedentary time (adolescents and parents), 2) cardiovascular fitness, 3) muscular strength, 4) motor ability, and 5) quality of life, will be evaluated using a similar general mixed modeling approach. The models will examine linear/nonlinear change over time (7 days at each of 0, 3, 6, 9, 12, 15, and 18 mos. for MVPA and sedentary time; 0, 6, 12, and 18 mos. for all other outcomes), overall group difference across time, and group difference in change. We will also longitudinally compare the percentage of adolescents achieving the 60 min./d MVPA (US recommendation) using generalized mixed modeling for repeated binary measures (yes/no in each observed day). In a secondary analysis, we will fit a general mixed model that includes cardiovascular fitness, muscular strength, motor ability, and quality of life as time-varying covariates, and assess their association with MVPA aggregated across months controlling for group.

Exploratory aims. If there are no between arm differences in the longitudinal change in MVPA across 18 mos., general mixed models will be fitted for the two arms combined to examine the association for the process variables/participant characteristics with MVPA. These variables include: attendance at group video (AO-adolescent; A+P-adolescent/parent) and education/support sessions (A+P only), self-monitoring of PA (AO-adolescent; A+P-adolescent/parent), parental use of Facebook page (A+P only), peer interactions/support during group PA sessions, adolescent self-efficacy, social support and barriers for PA, parental MVPA, beliefs and attitudes toward PA and parental time constraints, age, sex, and IDD diagnosis. However, if there is a significant group difference in MVPA, we will determine whether the previously listed process variables/participant characteristics explain/attenuate the intervention effect, i.e., moderation, by testing a 2-way interaction with the group effect and/or a 3-way interaction with the group-by-time interaction term. Some covariates will be measured only at baseline (age, sex, IDD diagnosis), some will be summarized across the trial (attendance at group video and education/support sessions, self-monitoring of PA, parental use of Facebook page, peer interactions/support during group PA sessions), while others will be assessed at specific time points (BMI, adolescent self-efficacy, social support and barriers for PA, parental MVPA, beliefs and attitudes toward PA and parental time constraints). Thus, we will carefully design our models to assure the appropriateness of the analysis. All analyses will be conducted using R and SAS 9.4 or higher.

Missing data. Missing due to either attrition, e.g., participant dropout or nonresponse, will be handled by multiple imputation, in which an expectation-maximization (EM) algorithm supplies prior estimates of missing values for a subsequent Monte Carlo Markov Chain (MCMC) procedure ⁶⁰. A sufficient number of imputed datasets will be created to ensure accurate recovery of missing data; and analysis results from each imputed dataset will be combined to make valid statistical inferences. All measured variables will be incorporated into the imputation process as auxiliary variables, thereby satisfying the missing at random (MAR) assumption ⁶¹.

REFERENCES

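### The 81% power applies a correlation based on a 3-month interval to all 21 days, including days in the same week, so it is unsupported for this structure and may be too high

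*Combined protocol and SAP*

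**What the plan says.** The Power paragraph, under Analysis plan and statistical power, sets the target as a between-arm difference "in the change of MVPA (0-6 mos.) of 10 min./d". The SD input reads "Assuming a conservatively large standard deviation for change in MVPA in both arms (35 min./d". The repeated-measures input is "the number of measurements ($n = 21$; 7 days at 0, 3, and 6 mos". One empirical correlation is offered: "The correlation between repeated measures of MVPA (3 mo. interval) in our pilot trial was" 0.22. The plan then says "To be conservative, we assumed a higher correlation", namely 0.25, and reports that G*Power gives 81% for the group effect with 57 adolescents per arm.

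The Primary aim analysis paragraph confirms that the 21 daily values enter the mixed model individually, with the error covariance structure chosen by model fit.

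The documents do not give a correlation between days of the same week. They do not say whether 0.22 relates single days or weekly means, and they do not state alpha.

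**The concern.** The 21 measurements are not evenly spaced. They form three clusters of seven consecutive days, three months apart. Days in one week share season, school timetable and stage of the intervention, so two of them would be expected to agree more closely than two days three months apart. The calculation gives both kinds of pair the same correlation, and the only value behind it is labelled as a 3-month one.

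The direction matters. The group effect compares person-level averages, and the more alike a person's days are, the less each extra day contributes. A same-week correlation set too low therefore inflates the power. The 81% is the stated justification for 114 participants and leaves little slack: entering the effect size as the rounded 0.14 already gives 79.2%, and no allowance is made for dropout.

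**Working it through.** **Inputs.** From the Power paragraph: difference 10 min/d, SD 35 min/d, N = 114, m = 21 days, r = 0.25 (pilot 0.22). Assumed: alpha 0.05, and the within-week correlation. The SD is taken as the plan uses it.

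**Plan's figure.** Effect size f = (10/35)/2 = 1/7 = 0.1429. For the G*Power between-factors test, λ = f²·N·m / (1 + (m − 1)r), referred to F with 1 and 112 df.

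- f²·N·m = (114 × 21)/49 = 48.86
- With r = 0.25, the denominator is 1 + 20 × 0.25 = 6, λ = 8.14, power 80.8%. This is the stated 81%.
- With r = 0.22, the denominator is 5.4, λ = 9.05, power 84.7%.
- With m = 3 and r = 0.25, power is 57.1%. The plan therefore used 21 days sharing one correlation, not three wave values.

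**Pairs of days.** There are 21 × 20/2 = 210 pairs, of which 3 × (7 × 6/2) = 63 lie within a week and 147 lie across waves. Each day has 6 same-week partners and 14 in other waves.

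**Two-level version.** Let r_w be the correlation between days of one week and r_b that between days of different waves. The denominator becomes D = 1 + 6·r_w + 14·r_b. The stated power is kept as long as D does not exceed 6.

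*Reading A: 0.22 is between single days.* With r_b = 0.22, D = 4.08 + 6·r_w, which reaches 6 at r_w = 1.92/6 = 0.32.

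*Reading B: 0.22 is between weekly means.* A weekly mean has variance proportional to (1 + 6·r_w)/7, so r_b = 0.22(1 + 6·r_w)/7 and D = 1.44(1 + 6·r_w). This reaches 6 at r_w = (6/1.44 − 1)/6 = 0.53. Had 0.25 been the weekly-mean value, the break-even would be 0.50.

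| Assumed r_w | A, r_b = 0.22 | A, r_b = 0.25 | B, 0.22 between weekly means |
|---|---|---|---|
| 0.3 | 81.5% | 78.8% | 93.2% |
| 0.4 | 77.7% | 75.1% | 87.9% |
| 0.5 | 74.0% | 71.6% | 82.3% |
| 0.6 | 70.6% | 68.3% | 76.8% |
| 0.7 | 67.3% | 65.2% | 71.6% |

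For scale, under reading A with r_b = 0.25, 80% power would take 130, 140 and 152 participants at r_w of 0.4, 0.5 and 0.6.

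**The case against.** A reader might infer that the power is simply too high, whatever the same-week correlation, provided it exceeds the 3-month one. The documents do not support that.

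- The documents' 3-month value is 0.22, and raising it to 0.25 leaves a margin. With 0.22 across waves, power is 83.5% at r_w = 0.25 and 81.5% at 0.30.
- If 0.22 is between weekly means, the stated power holds up to about 0.53, and below that it is understated.
- The two-level formula keeps one value for all cross-wave pairs. Of these, 7 × 7 = 49 are six months apart. If their correlation is lower than the 3-month value, power is somewhat higher than shown.

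A reader might also infer that 0.25 is not conservative at all. For the group effect it is conservative relative to the pilot value (80.8% against 84.7%). What is not shown is that this margin covers the same-week pairs.

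Nor is there an arithmetic error, since the plan's figure reproduces. The validity of the primary analysis is not at issue either, because the covariance structure is chosen by fit and equal correlation is not imposed on the model.

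All of this stands, and it limits the point to a conditional one. It does not supply the missing input: nothing in the plan tells the reader on which side of the break-even the trial lies.

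**Conclusion.** The point holds in conditional form. The 81% depends on giving 63 same-week pairs a correlation based on a 3-month interval, so it is unsupported for the structure of the data and may be too high. It is overstated if the within-week correlation exceeds about 0.32 (0.22 between single days) or about 0.53 (0.22 between weekly means). At a within-week value of 0.6 the power would be 70.6% or 76.8% respectively, and 68.3% with the planned 0.25 across waves between single days. These figures rest on alpha 0.05, on the plan's own effect size, and on within-week values that are assumed because the documents give none. This is an undocumented planning assumption about power.

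**What to change.** In the Power paragraph:

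1. State whether 0.22 is between single days or between weekly means.
2. Estimate the within-week correlation from the pilot's daily data and report it. The pilot described in the opening summary had 29 participants, so the estimate will be imprecise and a range is needed.
3. Restate the power for 57 per arm with 1 + 6·r_w + 14·r_b in place of 1 + 20·r, shown over that range, and state alpha.
4. Limit the claim of conservatism: 0.25 is conservative relative to the pilot's 3-month value, and same-week correlation is addressed separately.

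The cost is a recalculation and possibly a less favourable power figure. No change in sample size is asked for.

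### The 81% power is for a group effect averaged over baseline and follow-up days, not for the 10 min/d difference in 0-6 month change that the trial is said to be powered for

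*Combined protocol and SAP*

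**What the plan says.** In the combined protocol and SAP, under Analysis plan and statistical power, the Power paragraph opens: "This trial is powered to detect a between arm difference (AO vs. A+P) in the change of MVPA (0-6 mos.) of 10 min./d". The inputs are 57 adolescents per arm, 21 daily measurements (7 days at each of months 0, 3 and 6), an effect size f of 0.14 and a correlation of 0.25 among repeated measures.

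On the SD it says: "Assuming a conservatively large standard deviation for change in MVPA in both arms (35 min./d"). On the correlation it says: "The correlation between repeated measures of MVPA (3 mo. interval) in our pilot trial was" 0.22, and then "To be conservative, we assumed a higher correlation" of 0.25.

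The conclusion is that the sample "would provide 81% power to test overall between arm differences across time, i.e., group effect". A further sentence claims at least 80% power for the time-by-group interaction at f = 0.09, without converting that f to min/d.

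The Primary aim analysis paragraph gives the aim as comparing change from 0 to 6 months. Its mixed model examines a time effect, the "overall group difference across time, i.e., group effect, and group difference in change, i.e., time-by-group interaction".

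**The concern.** The target is a difference in change, but the power quoted is for a difference in average level over all 21 days. Randomised arms have an expected baseline difference of zero, so the 7 baseline days pull that average towards zero. The interaction sentence does address change, but at an effect size never tied to 10 min/d.

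The inputs also pull against each other. The 35 min/d cannot be both the SD of change and the SD of one day's value. A correlation observed across three months is applied to days in the same week. Raising the correlation is conservative for the group effect but not for a test of change.

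The Primary aim analysis lists both the group effect and the interaction and names neither as decisive. A null result could therefore be read as coming from an 81%-powered test of change, which the plan does not establish. If the group effect were used to decide the aim, it would dilute any real effect.

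**Working it through.** Two-sided alpha of 0.05 is assumed, since the plan states none; it reproduces the plan's figure. No loss of participants is assumed, as in the plan.

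**1. The plan's 81%.** With N = 114, m = 21, r = 0.25 and f = 10/(2 × 35) = 0.143, the between-groups repeated-measures F test has noncentrality f²·N·m/(1 + (m − 1)r) = 0.0204 × 114 × 21/6 = 8.14 on 1 and 112 df. Power is 80.8% (79.2% with f rounded to 0.14). So the 81% takes 35 as the SD of a daily value and needs an average gap of 10 min/d over all 21 days. With a zero baseline gap, months 3 and 6 would have to average 15 min/d.

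**2. The same test with no baseline gap and 10 min/d at month 6.** The month-3 values are assumptions.

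| Gap at months 0/3/6 | 21-day average | Power of group effect |
|---|---|---|
| 0/5/10 | 5.0 | 29% |
| 0/10/10 | 6.67 | 47% |
| 0/0/10 | 3.33 | 16% |

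**3. The interaction.** Noncentrality is f²·N·m/(1 − r). At f = 0.09 the 20-df test on 21 levels has 89% power, so that claim is sound on its own inputs. But f for the target is the root mean square of half the deviations from the average gap, divided by 35:

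- 0/5/10: f = 2.041/35 = 0.058, noncentrality 10.86
- 0/10/10 or 0/0/10: f = 2.357/35 = 0.067, noncentrality 14.48

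Both are below 0.09. Power is 44% and 59% as a 20-df test, or 85% and 94% as a 2-df visit-by-group test.

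**4. The change contrast itself (month 6 minus baseline).** If 35 is the daily SD, the between-visit correlation of days is 0.25 and same-week days correlate at rw, the SD of change in the 7-day mean is 35·√(2·((1 + 6rw)/7 − 0.25)). For rw = 0.25 this is 16.2, less than half of 35. The baseline-adjusted column uses the residual SD of the month-6 mean given baseline, which is SD of change × √((1 + R)/2), where R is the correlation between visit means.

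| Reading of the 35 min/d | SD of change | R | Unadjusted power | Baseline-adjusted power |
|---|---|---|---|---|
| SD of change | 35 | 0.25 (assumed) | 33% | 48% |
| Daily SD, rw = 0.25 | 16.2 | 0.70 | 90% | 94% |
| Daily SD, rw = 0.4 (assumed) | 24.0 | 0.51 | 60% | 72% |
| Daily SD, rw = 0.5 (assumed) | 28.1 | 0.44 | 47% | 60% |

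In the first row the residual SD is 35·√(1.25/2) = 27.7. The difference detectable with 80% power is then 14.6 min/d adjusted (13.1 to 17.1 for R from 0 to 0.7) and 18.5 min/d unadjusted.

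**5. Moving r from 0.22 to 0.25.** Power for the group effect falls from 84.7% to 80.8%. Power for change rises: 41.8% to 43.6% for the 20-df interaction (path 0/5/10), and 89.3% to 90.4% for the unadjusted contrast with daily SD 35.

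**The case against.** The best defence is that the 81% reproduces only with 35 as a daily SD, so its label may be a slip. On that reading the plan does well. A linear trend-by-group test has about 91% power for all three paths, because with equally spaced visits the linear contrast equals month 6 minus baseline. The 33% comes from an unadjusted two-point comparison that the plan does not propose; with baseline adjustment the low end is 48%.

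The Rationale also cites a small 6-month trial of parental training in Down syndrome, with MVPA changes of +18 min/d (n = 11, p = 0.01) and −7 min/d (n = 10, p = 0.30). If those are paired t tests (an assumption), the implied SDs of change are 18 × √11/3.17 = 18.8 and 7 × √10/1.10 = 20.1. Unadjusted power would be about 80% and 75%, or 94% and 91% with adjustment at R = 0.25. The Primary aim analysis also interprets only the interaction, which suggests that the interaction is the intended test.

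Much of this is fair. It shows that the sample may be adequate, that 33% is a pessimistic end, and that the effect of moving r is small. It does not connect the 81% to the target. It chooses one reading of the SD and one form of the interaction where the plan specifies neither, and two samples of about ten cannot settle the SD. Same-week correlations of 0.4 or 0.5 are also assumptions, but the plan gives no within-week figure to replace them.

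**Conclusion.** The concern holds. The stated power belongs to a group main effect that includes pre-treatment days, and with a zero baseline gap and 10 min/d at month 6 that test has 16% to 47% power. The interaction claim does not fill the gap, because 10 min/d corresponds to f of 0.058 to 0.067 against the stated 0.09.

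Power for the change is undetermined: 33% to 90% unadjusted and 48% to 94% baseline-adjusted across the readings tabulated. These figures rest on two-sided alpha of 0.05, complete data and the correlations shown. They do not establish that 114 is too few. The plan needs correcting because neither the deciding test for the primary aim nor its power is settled.

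**What to change.** Name one primary test: the 1-df between-arm difference in change in mean daily MVPA from baseline to month 6, from the mixed model with baseline arm means constrained equal. State that the group main effect including baseline days does not decide the primary aim.

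In the Power paragraph, say whether 35 min/d is the SD of change or of daily values. Give separate within-week and between-visit correlations from the pilot, state alpha and sidedness, and replace the 81% with the power or detectable difference for that contrast and model. For example, with an SD of change of 35 and visit correlation 0.25, the entry would read 48% power for 10 min/d, or 80% power for about 14.6 min/d.

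The cost is revised wording and one re-run of the calculation with pilot data. No extra participants are needed for the correction, but the stated power may become less favourable.

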Recruitment Procedures/Randomization. Organizations and community agencies serving individuals with IDD will be mailed/mailed an information brochure that describes the project. Additionally, we will use email list serves and media advertising (print, radio, internet) to target families living in the recruitment area. Potential participants will be asked to contact a member of the study team to obtain details about the program and complete the initial eligibility screening. Remote video chat sessions (Zoom) will be scheduled with interested participants and their parent to describe the project in detail, answer questions, verify eligibility, and to obtain parent consent and adolescent assent. Study staff will set up a virtual Zoom meeting that allows for remote video chat. Prior to the consent meeting families will be emailed a link for a KUMC REDCap survey they will contain the consent and assent documents. Additionally, Study staff will “share screen” the consent document and walk through each section, noting questions that arise, and answer these questions fully. Participants and adolescents will sign the consent/assent documents on the REDCap survey. Study staff will then print and provide the participant with a full-signed consent form for their records at the baseline testing meeting.

Adolescents age 18 and over, who are their own legal guardian, will sign their own consent. Project staff will fax/email a form to the potential participant’s PCP, which describes the eligibility criteria, study requirements, and request for clearance for participation. Parents of adolescents found to be ineligible will be provided with written materials describing available resources for assisting their adolescent with increasing PA. Cohorts of ~10-20 adolescent/parent dyads will be recruited and computer randomized. Adolescents will be stratified by sex and the presence or absence of DS, and sequentially randomized by the study statistician with equal allocation to the AO or A+P arms.

Intervention Components

The intervention components for the AO and A+P arms are identical with the exception of the parental involvement component.

MVPA recommendations

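### Baseline covariates enter the primary and secondary models only through significance tests on an open list, and the stratification factors (sex, Down syndrome) are not fixed terms in those models

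*Combined protocol and SAP*

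**What the plan says.** Recruitment Procedures/Randomization sets the strata: "Adolescents will be stratified by sex and the presence or absence of DS". The allocation method is described only in these words: "sequentially randomized by the study statistician with equal allocation to the AO or A+P arms". On timing, the same paragraph has: "Cohorts of ~10-20 adolescent/parent dyads will be recruited and computer randomized". Nothing is said about blocks.

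Analysis plan and statistical power, Baseline equivalence: "We will compare baseline characteristics, e.g., age, sex, race/ethnicity, BMI, IDD diagnosis, etc". Continuous variables are compared by t-test and categorical ones by chi-square or Fisher test. The consequence is that "Variables that demonstrate a significant nonequivalence will be controlled for in our analytic models". The plan's stated purpose is a more accurate estimate of the intervention effect. No significance level appears.

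Primary aim analysis: the mixed model has time, group and time-by-group terms, "controlling for day of the week (weekday/weekend) and baseline characteristics imbalanced between the groups". The secondary aims use a similar approach.

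Sex and IDD diagnosis are on the list to be tested, and they appear again in the exploratory aims as possible correlates or moderators. DS as such is in no analysis model.

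**The concern.** After proper randomisation, a significant baseline difference is a chance event. Using it to admit covariates has three consequences.

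- The covariate part of the primary model cannot be written down before the data are seen. With an open list and no level, two analysts could follow the plan and fit different models.
- The criterion is the wrong one for the stated purpose. Precision improves when a covariate predicts MVPA, whether or not it happens to be imbalanced.
- The rule works against the design. Stratification makes sex and DS balanced, and balance keeps them out of the model. If they predict MVPA level, an analysis that omits them reports a standard error that is too large for a stratified design.

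At stake are pre-specification and a little power, not the validity of the comparison.

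**Working it through.** **Inputs from the plan (Power paragraph).** N = 114 (57 per arm); difference 10 min/d; SD 35 min/d; 21 measurements; r = 0.25; stated power 81% for the overall group effect.

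**Assumptions, not in the documents.** Two-sided alpha 0.05; DS share 20-60%; R², the share of variance in person-level mean MVPA explained by sex and DS together; independent baseline tests in step 3. Blocked and unblocked allocation are both shown because the plan is silent.

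**1. Stated power.** f = 10/(2 × 35) = 0.1429. λ = N f² m/(1 + (m − 1)r) = 114 × 0.1429² × 21/(1 + 20 × 0.25) = 8.14. Noncentral F(1, 112) gives 80.8%, which matches 81%. (The rounded f = 0.14 gives 79.2%.)

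**2. How often the rule selects a stratification factor.** With 57 per arm and a factor near 50%, uncorrected Pearson chi-square gives p = 0.061 for 33 v 23 and p = 0.025 for 34 v 22, so a split of about 34 v 22 is needed.

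- No blocking, arms fixed at 57/57, factor totals 23, 46, 57 or 68 of 114 (exact hypergeometric): Pearson 3.5-6.1%, Fisher 1.8-3.5%.
- Blocks of 2-10 running through the trial (simulation, Pearson): 0 of 1,500 trials in each of 15 settings.
- Blocks of 2-10 restarting in each cohort of 10, 15 or 20: 0-3.7%.

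These treat DS as yes/no. If the tested variable is an IDD diagnosis with 3-5 categories including DS, simulated selection is 1.5-4.9%, depending on allocation.

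**3. Other variables entering by chance.** 1 − 0.95^k: three tests (age, race/ethnicity, BMI) 14%; five 23%; ten 40%. The length of the list partly decides the model.

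**4. Overall group-effect test.** For blocked allocation, sex and DS are taken as balanced.

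- Level without adjustment: 2(1 − Φ(1.96/√(1 − R²))).
- Power without adjustment: the estimator's variance is multiplied by (1 − R²) and the reported SE is unchanged, so power ≈ 1 − Φ((1.981 − √8.14)/√(1 − R²)).
- Power with adjustment: noncentral F(1, 110) with λ/(1 − R²), that is 8.57 at R² = 5% and 9.05 at 10%.

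For unblocked allocation, power without adjustment stays at 80.8%; with adjustment, λ is replaced by λ(1 − 2/113)/(1 − R²).

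| R² | Blocked: level unadjusted | Blocked: power unadjusted → adjusted | Unblocked: power unadjusted → adjusted |
|---|---|---|---|
| 0% | 5.0% | no gain | 80.8 → 80.1 (−0.7) |
| 5% | 4.4% | 81.5 → 82.7 (+1.2) | 80.8 → 82.0 (+1.2) |
| 10% | 3.9% | 82.1 → 84.7 (+2.6) | 80.8 → 84.0 (+3.2) |

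A simulation of 12,000 trials (DS 40%) compared never adjusting, always adjusting and the plan's rule. Blocked power was 81.4/82.8/81.4% at R² = 5% and 82.3/84.8/82.3% at 10%. Unblocked power was 80.4/81.8/80.5% and 80.4/83.8/80.8%. The rule recovers almost none of the available gain. Its level was 4.1% (blocked, both R²) and 5.0% or 4.7% (unblocked, R² 5% and 10%), so it is never inflated.

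**5. Time-by-group contrast.** On a complete 114 × 21 data set, the generalised least squares estimate is identical with and without sex and DS main effects (0.3268998911 both times): a term that is constant within a person cancels from change. Factor-by-time terms can help. With the contrast set at 80% power and sex and DS explaining 5% or 10% of the variance of change, simulated power rises from 79.8 to 81.0% and from 81.7 to 84.4% (blocked), or from 79.4 to 80.8% and from 80.8 to 83.6% (unblocked). If they explain none, there is no gain when blocked (79.2% both ways) and a small loss when unblocked (79.5 to 78.7%, Monte Carlo SE about 0.4 points).

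**The case against.** The strongest reply is that little follows for the primary question. The primary aim is a difference in change; baseline MVPA days are part of the response, so stable differences between persons already cancel. The gains concern the overall group effect, rest on R² values that no document supplies, and turn into a small loss if allocation is unblocked and the factors are not prognostic. All of this stands and limits the weight of the point. It does not answer the pre-specification problem, which needs no R².

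Four stronger readings are tempting, and the documents do not support them.

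- A reader might infer bias or a raised false-positive rate. The rule applied as written gives neither; inflation would need discretion over which variables are tested, and nothing in the plan shows that being used.
- A reader might infer that the whole primary model is unspecified. The outcome, time, group, interaction and weekday/weekend terms are fixed; only the baseline covariates are open.
- A reader might infer that sex and diagnosis are ignored. They are on the tested list and in the exploratory models.
- A reader might infer that BMI, a listed candidate, will be unavailable, because "During the COVID-19 lockdown height, weight, and waist circumference will not be collected". No passage says that baseline visits fell in the lockdown, and the Missing data paragraph provides multiple imputation using all measured variables. I place no weight on this.

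The selection rates also depend on Pearson or Fisher, and the plan allows either. Fisher selects the factors no more often than Pearson, which does not weaken the argument.

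**Conclusion.** The point holds as one of pre-specification and modest efficiency. The plan's rule leaves the baseline covariates to chance and to an open list, and it seldom admits the two factors used to stratify: roughly 2-6% per factor without blocking at an assumed 0.05, and rarely with blocks. For the overall group effect, omitting them costs about 1-3 power points and, under blocking, makes the test conservative (level about 4.4-3.9%), if they explain an assumed 5-10% of person-level mean MVPA. For the change contrast, main effects alone do nothing in complete balanced data; a gain needs factor-by-time terms and factors that predict change. Importance is low to moderate. The reading of the text is secure; the sizes are illustrations over assumed ranges.

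**What to change.** In the Baseline equivalence, Primary aim and Secondary aim paragraphs, replace the significance-based rule along these lines:

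- All primary and secondary adolescent models include sex and DS status as fixed effects, whatever the baseline comparison shows. Models of change also include sex-by-time and DS-by-time terms. Weekday/weekend stays in the models of daily accelerometer outcomes.
- No covariate is added to a main model because of a baseline test. Baseline comparisons between arms are descriptive.
- Adjustment for a closed, named set of other baseline variables is reported as a sensitivity analysis.

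This is a wording change. Sex and DS status must be known to randomise, so no new data are needed. The statistical downside is about 0.7 power points if allocation is unblocked and the factors turn out not to be prognostic.
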